DURATION OF THE STUDY: The total duration of study participation for each patient will be a maximum of 6 months consisting of: screening and baseline assessments; detoxification (13 days); and, follow-up evaluations conducted at 1, 3, and 6 months after enrollment. It is estimated that 2 patients will be enrolled per site per week with a total of 6 sites. Thus, the estimated length of enrollment is 30 weeks.

SAFETY ASSESSMENTS: Before any study procedures are performed, patients will be required to provide signed informed consent. All candidates for study enrollment will have a physical examination including vital signs and weight, medical history and history of prior medication use assessment, and psychiatric evaluation (ASI Lite) including a DSM-IV checklist for substance dependence, HIV risk assessment, and clinical laboratory studies (blood chemistry, hematology, Hepatitis B and C serology, and urinalysis) performed during screening/ baseline. All patients will have a 12-lead electrocardiograph (ECG). Females will be given a pregnancy test. Assessments of adverse events (AEs) and concomitant medication use will be performed daily during detoxification and at the one-month visit. Serious Adverse Events (SAEs) will be reported during the treatment and follow-up phases of the study.

OUTCOME ASSESSMENTS: Abstinence from opiates, amphetamines, cocaine, cannabinoids, methadone, and benzodiazepines will be assessed by urine drug screen measured at baseline, throughout detoxification, and at follow-up. Treatment retention will be calculated as the number of days each patient received his/her detoxification medication. The patient's status in the study will be tracked with a Study discharge report (SDR). The dispensing of ancillary medications will be tallied and grouped according to symptomology (several medications are permitted for treating anxiety, insomnia, nausea, etc.) and day during detoxification. Withdrawal symptoms will be assessed using the clinical opiate withdrawal scale (COWS), the adjective rating scale for withdrawal (ARSW), and visual analog scales (VAS) during detoxification and at follow-up (COWS and ARSW only). Additional measures of overall treatment effect will include a

shortened version of the Addiction Severity Index (ASI Lite), a client satisfaction questionnaire (CSQ), and SF-36 Health-related Quality of Life questionnaire administered at baseline and all follow-ups.

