14.0 ANALYTICAL PLAN

14.1 Statistical Hypotheses

Primary Efficacy Endpoint: It is hypothesized that BUP/NX detoxification, compared to clonidine, will be associated with a better treatment response. A treatment responder is defined as anyone who completes the 13-day detoxification and whose last urine specimen is negative for opiates. By combining treatment retention with opiate abstinence, a composite number is derived that is indicative of both the patients' tolerance to the treatment and the desired outcome of abstinence at the completion of a short-term detoxification procedure. Note that there is no issue concerning the handling of missing data when utilizing this definition of "responder." Patients who fail to either come in or provide a urine sample are, by definition, non-responders.

Other Primary Efficacy Endpoint: Other primary efficacy endpoints were selected to examine the effect of treatment on 1) opiate and other drugs of abuse abstinence throughout the detoxification period and during longer term follow-up, 2) withdrawal symptoms, 3) treatment retention, 4) safety, 5) patient satisfaction with the treatment and 6) extent of ancillary medications dispensed to provide a comprehensive overview of the clinical efficacy and safety of the two treatment regimens.

Hypotheses for the other primary outcome measures include that BUP/NX detoxification, compared to clonidine, will:

- 1. Increase the number and consecutive duration of opiate and all drug-free urine specimens during detoxification and follow-up.
- 2. Increase the number of days retained in treatment.
- 3. Decrease the amount of ancillary medications needed to treat withdrawal symptoms.
- 4. Lessen the severity of withdrawal symptoms as assessed by COWS, ARSW, and VAS.
- 5. Lessen the severity of dependence or abuse as assessed by ASI Lite.

6. Improve the quality of life as assessed by the SF-36 questionnaire and satisfaction with treatment (CSQ).

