14.2.2 Other Primary Outcomes

Other Primary outcomes include:

- 1. The number of urine specimens negative for opiates per patient (a maximum of 4 per patient).
- 2. The number of consecutive urine specimens negative for opiates per patient (maximum of 4).
- 3. The number of urine specimens negative for all drugs (opiates, methadone, cocaine, amphetamines, benzodiazepines, and cannabinoids) per patient (a maximum of 4 per patient).
- 4. The number of days retained in treatment (total days in treatment is the number of days since the start of treatment and the last day of treatment).
- 5. The frequency of dispensing of ancillary medications, by indication (anxiety or restlessness, bone pain or arthralgias, nausea, diarrhea, or insomnia).
- 6. The probability of remaining in treatment and being opiate-free at each urine collection.
- 7. The probability of remaining in treatment and being totally drug-free (negative urine tests for opiates, methadone, cocaine, amphetamines, benzodiazepines, and cannabinoids) at each drug collection.
- 8. The number and severity of adverse events.
- 9. The COWS score during treatment and 1-month follow-up.
- 10. The ARSW score during treatment and 1-month follow-up.
- 11. The VAS score during treatment.
- 12. The ASI Lite score during follow-up.
- 13. The CSQ score at the final visit.
- 14. The SF-36 score during follow-up.

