14.4 Analysis Plan

Baseline characteristics of groups will be generated using demographic data from intake questionnaires as well as the Addiction Severity Index. Information summarized will include gender distribution, age, years of use, route of administration, ethnic distribution, education, income, and ASI composite scores. Appropriate 2-sided *t*-tests or chi-square tests will be used to test for equivalence between groups. Inequalities between groups at baseline will be used as cofactors in analyses of outcome variables if related to outcomes.

Each of the primary and other primary outcome measures will be analyzed for the intent-to-treat population. The primary outcome measure is based on an intent-to-treat principle, and therefore cannot be analyzed in the evaluable population. The other primary outcome measures, however, will be analyzed for the evaluable population in addition to the intent-to-treat population. By examining the other primary outcome measures for the evaluable population, the long-term efficacy in treatment responders can be explored. Comparing results from the intent-to-treat and evaluable population analyses will also provide estimates of the effect of missing data. Major differences in the results, if any, will be further explored. While there is every intent to be complete in describing the analyses to be performed, it is not possible to anticipate every contingency, and some adjustments may be required to meet constraints posed by the structure of the data.

The primary outcome measure, treatment responders, will be compared between groups using the Chi-square statistic. Two-group two-tailed t-tests and analysis of variance (with repeated measures where appropriate) will be used to evaluate group differences in other primary outcomes, including retention, number of negative urines and number of consecutive negative urines, and frequency of ancillary medications dispensed. Survival analysis techniques including log- rank statistics will be used to evaluate treatment response over the duration of treatment and follow-up. Both retention in treatment and retention in treatment with negative urine tests for opiates will be evaluated. Repeated measures such as the ASI, VAS, COWS, ARSW will be evaluated using an appropriate repeated measures test such as generalized estimating equations.

Statistical tests will be two-sided, with alpha set at 0.05. Confidence intervals will be two-sided with a 95% confidence coefficient.

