14.6 Sample Size Estimate

Sample size and power calculations were made based on the primary outcome measure, treatment response. It was assumed that there would be 20% (maximally) treatment responders in the clonidine group and 30% treatment responders in the BUP/NX group. Using a Chi-Square test power analysis, and assuming a 2:1 buprenorphine:clonidine randomization ratio, an N of 360 is sufficient to detect the 10% difference in number of responders in the two arms with an alpha of 0.05 and a power of 90%. Therefore, the number of patients in the BUP/NX arm is proposed to be 240 and the number in the clonidine arm is to be 120.

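### Ancillary-medication dispensing is compared by t-test/ANOVA with no allowance for time in treatment, although retention is expected to be longer on BUP/NX

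*Protocol*

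**What the plan says.** - **Hypotheses (Protocol 14.1).** BUP/NX is expected to do two things at once: "Increase the number of days retained in treatment" (hypothesis 2) and reduce the ancillary medication needed (hypothesis 3).
- **Outcome (14.2.2, item 5).** How often ancillary medication is dispensed, by indication. No denominator is given.
- **Data (synopsis, 12.20, Table 1).** "The dispensing of ancillary medications will be tallied and grouped according to symptomology"; the same sentence goes on to group the tally by detoxification day as well. The log is kept daily, on days 1 to 13 only.
- **Test (14.4).** Two-group two-tailed t-tests and analysis of variance, with repeated measures where appropriate, for outcomes "including retention, number of negative urines and number of consecutive negative urines, and frequency of ancillary medications dispensed". The analysis is run in the intent-to-treat population and again in the evaluable population, which 14.3 limits to eligible patients who finish the 13 days. "Statistical tests will be two-sided, with alpha set at 0.05". No rate, offset or other use of time in treatment is mentioned.

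**The concern.** A patient who leaves on day 3 can contribute at most three days of dispensing; a completer contributes thirteen. If hypothesis 2 is true, BUP/NX patients have more days on which to be dispensed medication, and a comparison of totals mixes daily need with length of stay. The two hypotheses then work against each other: the larger the retention benefit, the worse BUP/NX looks on ancillary medication.

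Section 4.0 itself says that unrelieved withdrawal symptoms on clonidine can lead to early attrition. Patients in greatest need may therefore leave early and be counted as low users. A real reduction in need could be missed or appear with the wrong sign.

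**Working it through.** **No plan figure to reproduce.** The only power statement (14.6) concerns treatment responders, not this outcome. From it I take only the group sizes, 240 and 120; alpha is 0.05 two-sided (14.4). Dispensing rates, their spread and retention by arm are not in the protocol, so everything below is assumed and shown as a range.

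**1. Direction.** With constant daily need λ, expected total = λ × mean stay. Hence ratio of totals = daily rate ratio × ratio of mean stays, and the sign reverses when the rate ratio exceeds the inverse of the stay ratio.
- 11 vs 8 days: break-even 8/11 = 0.73, so any true daily reduction below 27% shows as more medication on BUP/NX. A 20% reduction gives 0.8 × 1.5 × 11 = 13.2 vs 1.5 × 8 = 12.0.
- 10 vs 8.5 days: break-even 0.85, so reductions below 15% reverse.

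**2. False harm with flat, equal need.** Assume λ = 1.5 per day, gamma variance 0.5 between patients, and a fraction f staying 13 days with the rest uniform on days 1-12 (mean 6.5). Then f = (mean − 6.5)/6.5: 0.692 for 11 days, 0.231 for 8.
- Variance of a patient's total = λE[T] + λ²(1.5 E[T²] − E[T]²), with E[T²] = 169f + 54.17(1 − f).
- BUP/NX, 11 days: E[T²] = 133.67; variance = 16.5 + 2.25(200.5 − 121) = 195.4.
- Clonidine, 8 days: E[T²] = 80.67; variance = 12 + 2.25(121 − 64) = 140.3.
- Pooled variance = (239 × 195.4 + 119 × 140.3)/358 = 177.1; t-test SE = √(177.1 × (1/240 + 1/120)) = 1.488; true SE = √(195.4/240 + 140.3/120) = 1.408.
- Difference = 16.5 − 12.0 = 4.5. Chance of significant harm ≈ Φ((4.5 − 1.96 × 1.488)/1.408) = Φ(1.13) ≈ 87%.
- The same steps at 10 vs 8.5 days: variances 181.5 and 152.3, difference 2.25, Φ((2.25 − 1.96 × 1.465)/1.423) = Φ(−0.44) ≈ 33%.

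The simulated values agree: 87% and 33%.

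**3. Sensitivity (simulation, equal daily need).**

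| Setting | False significant harm to BUP/NX |
|---|---|
| 11 vs 8 days, flat need | 87% |
| 11 vs 8, linear decline | 69% |
| 11 vs 8, steep decline | 40% |
| 10 vs 8.5, flat to steep decline | 33% to 14% |
| 10 vs 8, flat | 56% |
| 9 vs 8, flat | 19% |
| 11 vs 8, flat, gamma variance 1.0 | 65% |
| Equal stay | about 2.5% (nominal) |

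The error returns to nominal when stays are equal, so differential retention is the cause. A different dropout model (constant daily dropout, completion 60% vs 30%, one dispensing per day) gives 74%.

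**4. Lost power.** With a true 40% lower daily need, the t-test on totals finds the benefit in 47% of trials at 11 vs 8 days, against 99% when both arms stay 8 days.

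**5. Is a log(days) offset enough?** Not if need falls over the 13 days, because early leavers contribute mainly high-need days. Under steep decline with a 20% reduction, totals at 11 vs 8 days are 14.2 vs 15.0. Equal need therefore corresponds to 14.2/0.8 = 17.75 vs 15.0, and the rate ratio per day is (17.75/11)/(15.0/8) = 1.61/1.88 = 0.86, an apparent benefit where none exists. The offset analysis falsely favours BUP/NX in 15% of trials under linear decline and 44% under steep decline. A comparison adjusted for study day held 2-3% in each direction in every setting.

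**The case against.** **The protocol does not fix a raw total.** Items 1 to 3 of 14.2.2 are explicitly per patient; item 5 only speaks of frequency. The tally is also grouped by day, repeated-measures analysis of variance is available, and scaling can be left to a statistical analysis plan. This stands in part, and it makes the size conditional on totals being compared. But 14.4 does name the tests for this outcome, and neither there nor in 14.2.2 does time in treatment enter. The repeated-measures option is not assigned to this outcome, and in its classical form it drops patients with missing days or needs a rule for days after dropout.

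**The completer analysis equalises exposure, and differences between populations will be explored.** It may reveal a discrepancy, but completion happens after randomisation and is expected to differ by arm, so it cannot supply the unbiased comparison.

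**The size is fragile.** True. It rests on assumed rates, models a total rather than single indications, and shrinks if need declines. At 0.3 per day for a single indication and 10 vs 8.5 days, false harm is 25%. Under steep decline, a true 20% reduction at 11 vs 8 days (14.2 vs 15.0) does not reverse.

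**Adverse events.** A reader might infer that "The number and severity of adverse events" (14.2.2, item 8) suffers the same flaw. The documents do not support that. Section 14.4 names no t-test for adverse events, 14.5 describes only frequency tables, and collection continues at the one-month visit (12.10, 13.6), so the window does not simply close when treatment ends.

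**Conclusion.** The point holds for ancillary medication. As written, 14.4 tests hypothesis 3 without regard to time in treatment, while hypothesis 2 predicts that this time will differ. If totals are compared, the bias runs against BUP/NX and grows with the retention difference: about 40-87% false significant harm at mean stays of 11 vs 8 days and 14-33% at 10 vs 8.5. This assumes 1.5 dispensings per day, gamma variance 0.5 and equal daily need; the spread comes from how need declines. With equal retention there is no bias.

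It does not follow that the sign will reverse in this trial; that depends on rates and stays the protocol does not give. The primary responder comparison is unaffected. The outcome is one of fourteen other primary outcomes, but it carries a directional hypothesis, so the plan should be corrected.

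**What to change.** In 14.2.2 item 5 and 14.4:

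- Define the outcome as daily dispensing, by indication, on each day a patient is in treatment.
- Compare arms with a day-level count or binary model, for example generalized estimating equations clustered by patient, with study day as a factor. Report the rate ratio with its 95% confidence interval.
- Present it beside retention by arm.
- State which days count as in treatment. The synopsis counts days on which medication was received, whereas 14.2.2 item 4 counts from the start to the last day of treatment.
- Do not rely on a single log(days) offset or on the completer analysis as the correction.

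The cost is analysis wording only: the daily ancillary log (12.20) and the dosage log (12.19) already hold the data. The small downside is that the estimate is conditional on being in treatment, so it must be read together with retention and not as a stand-alone effect.

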In designing a buprenorphine detoxification program, three main objectives should be met. First, patient compliance and treatment retention should be maintained. Second, opioid abstinence should be achieved. Third, minimal abstinence symptomology should result from the dose reduction schedule in order to minimize the risk for relapse. The purpose of this study is to determine the clinical utility of BUP/NX as compared to clonidine (an alpha-2 adrenergic agonist) for short-term opiate detoxification with treatment initiated in inpatient settings. Clonidine hydrochloride has been previously shown to be a safe and effective medication for detoxifying individuals from narcotics (Gold et al., 1980). Advantages of clonidine include its non-narcotic status and accessibility to primary care providers in both inpatient and outpatient settings. However, side effects such as postural hypotension and sedation (Charney et al., 1981; Gossop, 1988) or unrelieved withdrawal symptoms such as insomnia can lead to early patient attrition and be particularly difficult to manage on an outpatient basis. Although in controlled clinical trials buprenorphine appeared to be more effective than clonidine for alleviating withdrawal symptoms (Nigam et al., 1993; O'Connor et al., 1997), more research is needed comparing the relative effectiveness of these two medications in community treatment settings. In particular, studies are needed in community-based clinics that use the product formulation of buprenorphine (i.e., the BUP/NX tablet) anticipated to be marketed.

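### Unweighted GEE, the example method for COWS, ARSW and VAS, can understate a BUP/NX benefit if dropout follows symptoms, and the stated completer comparison would not measure this

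*Protocol*

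**What the plan says.** - **Hypotheses (14.1).** BUP/NX, compared with clonidine, is expected to "Lessen the severity of withdrawal symptoms as assessed by COWS, ARSW, and VAS" and to "Increase the number of days retained in treatment". COWS, ARSW and VAS are items 9 to 11 of the other primary outcomes (14.2.2).
- **Analysis (14.4).** These outcomes are analysed in the intent-to-treat population and again in the evaluable population. The only method named for the scales is an example: "Repeated measures such as the ASI, VAS, COWS, ARSW will be evaluated using an appropriate repeated measures test such as generalized estimating equations". No working correlation is given. "Statistical tests will be two-sided, with alpha set at 0.05".
- **Dropout (4.0).** On clonidine, side effects such as hypotension and sedation, or "unrelieved withdrawal symptoms such as insomnia can lead to early patient attrition".
- **When scores exist (11.8, 12.11, 12.12, 12.14, Table 1).** They are taken daily or at each clinic visit during detoxification. A patient who terminates early has the day 13 or 14 assessments done at the final visit. COWS and ARSW are repeated at 1 month.
- **Missing data.** Counting a missing patient as a failure applies only to the responder endpoint (14.1). Section 14.4 states that setting the intent-to-treat results against the evaluable results will estimate the effect of missing data. Section 14.3 limits the evaluable set to eligible patients who complete the 13 days. Section 14.5 adds a comparison of missing-observation counts by arm.

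**The concern.** The protocol's own premises tie dropout both to treatment arm and to the quantity being measured. Unweighted GEE is generally valid only when missingness is unrelated to the scores. With an independence working correlation it compares, day by day, the mean scores of patients still attending. If clonidine patients with worse scores leave sooner, those who remain look milder than the group that was randomised. The bias then runs against BUP/NX. Three listed outcomes rest on this analysis. The check offered in 14.4 conditions on completion, which happens after randomisation and is expected to differ by arm.

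**Working it through.** **The plan's own figures.** None concerns the withdrawal scales: no effect size, SD or dropout rate is given. The only calculated figure is 90% power for responders (14.6). From "It was assumed that there would be 20% (maximally) treatment responders in the clonidine group and 30% treatment responders in the BUP/NX group" with 120 and 240 patients, power = Φ[(0.10 − 1.96 × 0.0494)/0.0470] = Φ(0.066) = 52.6%, where 0.0494 is the pooled and 0.0470 the unpooled standard error. So 90% is not reproduced. That is a separate matter and does not bear on this point.

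**Why the working correlation matters.** Let Y be the score on day t and R = 1 if it is observed. Independence GEE fits an ordinary regression to the observed person-days, so it targets E(Y | arm, t, R = 1). This equals E(Y | arm, t) only if R is unrelated to Y given arm and day. A fit that uses the within-patient correlation correctly lets earlier scores inform the days after dropout. It stays valid when dropout depends on observed scores.

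**Inputs from the protocol.** 240 versus 120 patients, 13 daily scores, two-sided alpha 0.05. **Assumed:** completion rates, dropout slopes, correlation and true effect. Dropout model: logit(daily dropout) = a + b × score, with a and b allowed to differ by arm. Below, a positive estimate favours BUP/NX.

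**Setting A.** True benefit 0 or 0.30 SD; dropout depends on the previous observed score; 300 trials per cell; no final-visit score. Slopes are 0.7 logit per SD in both arms (equal), or 0.3 BUP/NX and 1.0 clonidine (unequal).

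| Completion, BUP/NX / clonidine | Slopes | Independence GEE: rejection, no true difference | Independence GEE: power at 0.30 SD |
|---|---|---|---|
| 45/25% to 75/50% | equal | 8–13% | 67–82% |
| 45/25% to 75/50% | unequal | 28–53%, nearly all favouring clonidine | 22–59% |
| 85/70% | equal | 5–6% | 77–90% (both slope settings) |
| 85/70% | unequal | 12–17% | as above |

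Complete data gave 92–98% power. Up to 75/50% completion, the independence estimate fell from 0.30 to 0.11–0.25 SD. Generalised least squares with the true covariance, standing in for a mixed model, gave 3–8% rejection and 89–97% power. Exchangeable GEE was close to unbiased. Monte Carlo error at a true 5% is √(0.05 × 0.95/300) = 1.3 points, so 5–6% is essentially nominal.

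**Setting B.** True benefit 0.50 SD; completion about 31–56% BUP/NX and 15–35% clonidine; dropout on the current or previous score, with and without a final-visit score; 40–60 trials per cell. The completer column comes from the AR(1) runs only.

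| Dropout depends on symptoms | Independence GEE | Exchangeable GEE | Completers only |
|---|---|---|---|
| not at all | 0.48–0.52 | 0.48–0.52 | about 0.50 |
| equally in both arms | 0.38–0.44 | 0.48–0.51 | about 0.30 |
| more in clonidine | 0.20–0.30 | 0.42–0.52 | about 0 |
| in clonidine only | −0.16 to 0.20 | 0.34–0.53 | −0.24 to −0.35 |

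In the last row the completer analysis was significant for clonidine in 47–88% of trials. The final-visit score helps. With clonidine-only dropout on the current score and AR(1) data, at the two slopes tried, it moved independence GEE from 0.11 and −0.01 to 0.20 and 0.15.

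**Setting C.** True benefit 0 or 0.30 SD; about 60/40% completion; baseline-adjusted; 100 trials per cell. Independence GEE shrank 0.30 SD to 0.22–0.27 SD. With no true difference and unequal slopes it rejected in 15–21% of trials. Exchangeable GEE and the correct-covariance fit stayed near 0.30 SD.

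**The case against.** The strongest reply is that 14.4 asks for an appropriate test and gives GEE only as an example. A mixed model or weighted GEE already fits that wording, nothing selects independence, and a statistical analysis plan would normally settle the rest. This stands in part: an unstated working correlation or missing-data method is no fault in itself. What remains is that the one method named suits the protocol's dropout premise poorly, and that 14.4 makes a positive claim about the completer comparison that does not hold.

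Other objections also have force. Section 4.0 says attrition can follow, and names side effects as well as withdrawal; dropout from hypotension need not track COWS. Treatment starts in hospital and ancillary medication is open to all. The early-termination visit recovers some information, and Setting A left it out. No simulation modelled the 1-month scores. The largest figures need dropout slopes that differ by arm, which no section supplies. The likelihood fit was given the true covariance, which no analyst has.

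A reader might infer that the intent-to-treat analysis would reverse a true BUP/NX benefit. The evidence does not support that. Setting A's estimates under a true benefit stayed positive (0.11–0.25 SD). Setting B changed sign only with clonidine-only dropout, working independence and no final-visit score, and then by at most 0.16 SD. Clear reversal belongs to the completer analysis. Nor does GEE compare completers alone, since it uses every patient's scores up to dropout.

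**Conclusion.** The concern holds in limited form. If dropout follows earlier symptom scores, unweighted GEE can attenuate or hide a true BUP/NX benefit on COWS, ARSW and VAS, particularly with independence. With no true difference it can favour clonidine too often. The size rests on assumed dropout. It is modest with equal slopes or high completion. With an exchangeable correlation it is small, except where dropout depends on current scores that are never observed: there 0.50 SD fell as low as 0.34 SD.

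The point about the check is firmer. Comparing intent-to-treat with completers does not estimate the effect of missing data, because completion is itself an outcome of treatment. In the simulations the completer result was further from the truth than the analysis it was meant to check whenever dropout followed symptoms.

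The change is worth making; confidence is medium. The responder endpoint is unaffected, since there a missing patient counts as a failure. The ASI at follow-up was not examined and no claim is made about it.

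**What to change.** In 14.4, for COWS, ARSW and VAS:

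1. Replace the GEE example with a likelihood-based mixed model for repeated measures, with terms for arm, day, arm by day and baseline score, and a flexible covariance. Use all observed scores, entering the early-termination visit at its actual study day. Alternatively, keep GEE but weight it by the inverse probability of still attending, modelled from arm and previous scores.
2. Add one sensitivity analysis that assumes worse scores after dropout.
3. Remove the statement that comparing intent-to-treat with evaluable results estimates the effect of missing data.

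The cost is wording and a little more analysis; no new data or patients are needed. The downside is reliance on the covariance model and on missingness being explained by observed scores. The sensitivity analysis probes the second. On the first, an unstructured covariance over 13 days has 13 × 14/2 = 91 parameters and was not fitted here, so a simpler flexible structure should be named as a fallback, with robust standard errors.

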12.13 Addiction Severity Index (ASI Lite)

The ASI Lite is a standardized, multidimensional, semi-structured, comprehensive clinical interview which provides clinical information important for formulating treatment plans as well as problem severity profiles in six domains commonly affected in substance abusers (McLellan et al., 1985). The domains covered are chemical abuse (alcohol and drug), medical, psychiatric, legal, family/social and employment/support. Composite Scores for each problem domain are derived mathematically and used as change measures or outcome indicators as a function of treatment intervention. This instrument also provides clinically necessary information on whether the patient is at imminent risk for suicidality, thus permitting evaluators to implement any needed immediate and/or early intervention strategies. A revised version of the ASI Fifth Edition, 1997 version (ASI Lite), that includes only those questions used to derive the composite scores along with some demographic information will be administered by a research staff member having at least a bachelor's degree in the social sciences or equivalent training and experience as determined by the site's investigator. Composite

scores will be calculated according to the procedures described by McGahan *et al.* (1982), Carroll *et al.* (1994). The ASI Lite will be administered before study drug administration and at each of the 1, 3, and 6 month follow-up visits.

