12.17 SF-36

The SF-36 is a 36-item, patient administered instrument examining health-related quality of life changes as a function of treatment (Ware and Sherbourne, 1992). Each item is rated on a 5 point scale. The SF-36 will be completed at baseline and all follow-up visits.

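### Section 14.4 ties baseline adjustment of the withdrawal, ASI Lite and SF-36 scores to a between-arm test instead of prespecifying each scale's own baseline as a covariate

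*Protocol*

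**What the plan says.** **Baseline measurement.** Table 1 (Time and Events Schedule) marks COWS, ARSW, VAS, ASI Lite and SF-36 in the screening/baseline column. Section 12.13 confirms this for the ASI Lite: "The ASI Lite will be administered before study drug administration and at each of the 1, 3, and 6 month follow-up visits". Section 12.17 does so for the SF-36: "The SF-36 will be completed at baseline and all follow-up visits". For the VAS, section 12.14 mentions only daily completion during detoxification, so its baseline rests on Table 1.

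**Outcome definition.** Section 14.2.2, items 9 to 12 and 14, defines these outcomes as scores after treatment starts, not as change from baseline. Examples are "The COWS score during treatment and 1-month follow-up" and "The SF-36 score during follow-up".

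**Model.** Section 14.4: "Repeated measures such as the ASI, VAS, COWS, ARSW will be evaluated using an appropriate repeated measures test such as generalized estimating equations". No model terms are listed, and the SF-36 is not named in that sentence, although its list is only illustrative.

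**Covariate rule.** Section 14.4 summarises baseline characteristics, naming "gender distribution, age, years of use, route of administration, ethnic distribution, education, income, and ASI composite scores". It then says "Appropriate 2-sided *t*-tests or chi-square tests will be used to test for equivalence between groups", and follows with: "Inequalities between groups at baseline will be used as cofactors in analyses of outcome variables if related to outcomes". This is the only statement in the section on how a baseline variable reaches an outcome model.

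**The concern.** The baseline value of a scale is often among the best predictors of its later values. Here it is collected on every patient, yet its use depends on whether a significance test happens to show a difference between the arms. That creates two problems.

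- **Lost precision.** The reason to adjust for a prognostic baseline score is to remove between-patient spread from the error term. That gain exists whether or not the arms differ, and the rule gives it up whenever no difference is flagged.
- **An analysis model not known in advance.** Which covariates enter is decided by the trial's own data.

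Hypotheses 4 and 5 in section 14.1 (withdrawal severity, dependence severity) and the quality-of-life part of hypothesis 6 rest on these scales, and the protocol calls them other primary outcomes. No COWS threshold limits entry: sections 9.1 and 11.3 ask only for reported withdrawal symptoms, physical dependence and mild withdrawal before the first dose. Entry severity can therefore vary.

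**Working it through.** The protocol gives no power or precision figure for these scales, so there is none to reproduce. Its only sample-size figure concerns the responder outcome and has no bearing here.

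**Inputs from the protocol.** 240 BUP/NX and 120 clonidine (14.6); two-sided alpha 0.05 (14.4).

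**Assumptions.** Baseline-outcome correlation ρ of 0.3, 0.5 or 0.7, with 0.2 as a low case; effect of 0.30 SD; complete data; normal approximation. The protocol gives no correlation, standard deviation or target effect for these scales.

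**Step 1: how often the rule adjusts.** Under randomisation any baseline difference is due to chance, so a test at 0.05 is significant for any one variable about 5% of the time. The further condition, that the variable be related to outcome, can only lower this. For a given ASI composite, the gain is forgone in about 95% of such trials.

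**Step 2: variance of a single post-baseline comparison.** In SD units:

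unadjusted SE = √(1/240 + 1/120) = 0.1118

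adjusted SE = 0.1118 × √(1 − ρ²)

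power = Φ(0.30/SE − 1.96)

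Unadjusted: 0.30/0.1118 = 2.683, and Φ(0.723) = 76.5%.

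| ρ | 1 − ρ² | Variance cut | 0.30/SE | Power | Equivalent unadjusted N = 360/(1 − ρ²) |
|---|---|---|---|---|---|
| 0.2 | 0.96 | 4% | 2.739 | 78% | 375 |
| 0.3 | 0.91 | 9% | 2.813 | 80% | 396 |
| 0.5 | 0.75 | 25% | 3.098 | 87% | 480 |
| 0.7 | 0.51 | 49% | 3.757 | 96% | 706 |

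**Step 3: mean of the three follow-up visits (ASI Lite, SF-36).** Assume one common correlation ρ among baseline and all visits. The variance of the mean is v = (1 + 2ρ)/3, and it becomes v − ρ² after adjustment. At ρ = 0.5, v = 0.667 and v − ρ² = 0.417, a ratio of 0.63. The ratio is 0.83 at ρ = 0.3 and 0.39 at ρ = 0.7. For an assumed 0.25 SD effect at ρ = 0.5:

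- unadjusted: 0.25/(0.1118 × √0.667) = 2.74, power 78%
- adjusted: 0.25/(0.1118 × √0.417) = 3.46, power 93%

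**Step 4: chance imbalance.** The baseline difference has SD 0.1118, so its 95% range is 1.96 × 0.1118 = ±0.22 SD. Unadjusted, this moves the estimate by up to ρ × 0.22, or about ±0.07 SD (ρ = 0.3) to ±0.15 SD (ρ = 0.7). This is the same loss as in step 2 seen from another side, not an additional one.

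**The case against.** The strongest reply is that silence is not exclusion. Section 14.4 names a family of methods as an example and lists no terms at all, not even treatment or visit. Model terms for outcomes other than the responder endpoint are commonly left to the SAP, which is not at hand. This stands against a stronger reading that a reader might infer, namely that the models carry no baseline score. The protocol does not say that. It does not defend the test-then-adjust rule, which the protocol itself states for analyses of outcome variables. An SAP that prespecified own-baseline adjustment would depart from it.

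A reader might also infer that baseline COWS, ARSW, VAS and SF-36 can never enter a model. That goes too far. Section 14.5 calls the same list of characteristics a minimum, so further variables may be compared, and ASI composites can enter as the rule stands. What remains is that four of the five scales are not named and that entry depends on a test.

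Two other inferences are unsupported. Chance imbalance does not bias the unadjusted estimate on average under randomisation; it adds variance. And nothing suggests that baseline would be modelled as one of the repeated responses, which would dilute a group main effect: section 14.2.2 defines these outcomes as post-baseline scores.

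Finally, the gain may be small for COWS, ARSW and VAS. All patients are in withdrawal at entry and are then scored under treatment aimed at that withdrawal, so the correlation may be low. Dropout would also lower the power levels. Both points stand.

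**Conclusion.** The point holds as a criticism of a rule that the protocol states, not as a claim that baseline is left out. Section 14.4 makes adjustment for a scale's own baseline depend on a between-arm test that, at 0.05, flags any one variable about 5% of the time, and it does not name four of the five scales for that test. Followed as written, it usually forgoes precision from data already collected.

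The cost ranges from slight to substantial: 4% of variance at ρ = 0.2, and 9%, 25% or 49% at 0.3, 0.5 or 0.7. The correlations, the effect sizes, complete data and, in step 3, the common correlation are all assumptions; only the arm sizes and alpha come from the protocol. The responder analysis is not affected. The change is worth making because it costs almost nothing and also fixes the model in advance.

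**What to change.** In 14.4, replace the test-then-adjust rule for these scales with a statement that each repeated-measures model for COWS, ARSW, VAS, the ASI Lite composites and the SF-36 includes that instrument's own baseline score as a prespecified covariate, whatever the balance tests show. State that the response is the post-baseline scores only, with treatment, visit and treatment-by-visit terms. Name the SF-36 explicitly, since the present sentence does not. Any SAP should carry the same wording.

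The cost is one or two sentences and no new data. The only added burden is a simple rule, fixed in advance, for a patient whose baseline score is missing.
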